## 9.6 Data Management

Before starting the PASS, the sites will be trained on the background and objectives of this PASS and on ethical as well as regulatory obligations.

A global contract research organisation (CRO) will develop an EDC system and will provide quality assurance, verification of the data collection, data analysis and data transfer to the MAH. All outcome variables and covariates will be recorded in a standardised eCRF. After data entry, missing or implausible data will be queried and the data will be validated. A check for patients being documented multiple times will be done.

The latest Medical Dictionary of Regulatory Activities (MedDRA) version will be used for coding of medical history, concomitant diseases, and AEs. Prior and concomitant medication/treatment will be coded with the most current version of the World Health Organization (WHO) Drug Dictionary (coding system version numbers will be stated in the SAP). The SAP is kept as a stand-alone document and listed in section 15.1.

A Data Management Plan (DMP) will be prepared and contains detailed information on checks for completeness, accuracy, plausibility, and validity. This plan will also specify measures for handling of missing data and permissible clarifications. The DMP is kept as a stand-alone document and listed in section [15.1](#).

National and international data protection laws as well as regulations on PASS will be followed.

## **9.7 Data Analysis**

### **9.7.1 Statistical Considerations**

Statistical analyses will be of an exploratory and descriptive nature. All variables will be analysed descriptively with appropriate statistical methods: categorical variables by frequency tables (absolute and relative frequencies) and continuous variables by descriptive statistics (i.e., number of patients, mean, standard deviation, minimum, median, quartiles, and maximum). Continuous variables will be summarised by absolute value and changes from baseline per analysis time point, if applicable.

The sample size and disposition information by analysis time point will be displayed in a frequency table.

Procedures and routines for capturing associated data strongly depend on country specific standards of care, type of healthcare provider, and insurance status of patients. Therefore, missing data in non-interventional research are informative categories indicating coverage of services.

No imputation of missing information will be applied. The number and frequency of patients with missing data will be presented as separate category.

All issues concerning patient data validity, data consistency checks, and permissible data modifications will be described in detail in the DMP. All statistical issues including calculated variables and the proposed format and content of tables will be detailed in the SAP. The SAP will be finalised before study database lock.

Information on the interim analysis is presented in section [9.7.5](#). The final data analysis will be performed after the study has been completed and the database has been declared to be clean.

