## 6 Milestones

Milestone	Planned date
Start of data collection (FPFV)	Q1/Q2 2026
End of data collection (LPLV)	Q3/Q4 2029 The scheduled study duration per country includes a patient recruitment phase of up to 18 months and an individual prospective observational period for as long as feasible within the scheduled study timeframe. In case the observational period per country is prolonged, data collection will be prolonged as well.
Progress reports 	Progress reports related to the state of PASS recruitment will be part of every PSUR. The PSUR will be submitted as per the EURD list requirements.
Interim report	First interim report is expected in Q3/Q4 2028. Further interim analyses will be provided every two years unless the final report is delivered until Q4 2029.
Registration in the EU PAS register	Before start of data collection.
Final report of study results	December 2030 One year after end of data collection.

 Only if agreed with authorities.

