#### **9.7.3.3 Analysis of Primary Endpoint**

The primary objective will only be assessed in users with the long-term treatment (>12 months) and where z-scores of lumbar spine, total hip, or femoral neck are available. For rates of events of BMD z-scores below the age-related threshold of -2 standard deviations, the number and percentage of patients with these events will be provided including 95% CIs.

The aggregated number, frequency of DXA scans, anatomic site of DXA scan, machine type, and imaging parameters of DXA scans during the observational period will be analysed by descriptive statistics. If results of DXA scans can be interpreted in a categorised way, shift tables for the change from baseline, will be provided, where available. If images of the DXA scans can be provided by the doctors, they will be reviewed by 1 independent expert for their suitability and included in an additional sensitivity analysis.

Sensitivity analyses using different criteria (e.g., machine type) to select DXA scans that ensure their comparability will be performed to evaluate the primary endpoint if the sample size allows (e.g., if more than 30 patients remain after selection of suitable cases) and will be further detailed in the SAP.

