#### **9.7.3.5 Analysis of Other Information**

Descriptive statistics will be provided for alcohol/nicotine/drug/stimulant consumption.

Frequency tables with incidences and EAIR of AEs, SAEs, ADRs, and SADR will be provided on MedDRA SOC and PT level. The incidence and EAIR will be provided including 95% CIs. Listings of special situations (drug interactions, medication abuse, medication misuse, medication overdose, medication errors, unexpected therapeutic, or clinical benefit from product use, pregnancy or lactation exposure with the product, lack of efficacy, off-label use, and occupational exposure) will also be provided.

Further details will be specified in the SAP, which will be finalised before study database lock.

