#### **9.7.5 Interim Analysis**

The first interim report is expected in Q3/Q4 2028. Further interim analyses will be provided every 2 years unless the final report is delivered until Q4 2030.

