### **11.3 Documentation**

All AEs under exposure to Yselty® that have been reported by the patient to the physician (i.e., AEs, SAEs, ADRs, SADR, special situations) will be documented on the AE Report form in the eCRF/EDC system. Assessment on seriousness and relationship to product, treatment duration, action taken, and outcome of the event will be provided by the treating physician, who will also be responsible for following up on the outcome of SAEs, if this information is not available when first reported. Where required, physicians might be contacted directly, per the MAH's internal follow-up procedure, to obtain further information.

In addition, for selected events (see section 9.4), the MAH will utilise the targeted follow-up questionnaires, where applicable, as per the latest version of the RMP (see section 15.1). The purpose is the ongoing monitoring and safety evaluation of these events.

The documentation of any event within the eCRF ends with the completion of the follow-up of the patient or until it is no longer possible (e.g., lost to follow-up, death, withdrawal). In case of discontinuation of Yselty® for any reason, all events will be collected that occurred up to 30 days after the last administration. Since the  $t_{1/2}$  elimination time of linzagolix is 15 hours, exposure has well ended after 30 days. However, patients who discontinued treatment with Yselty® but experienced BMD decrease or osteoporosis during the study will continue to be followed up unless they have completely withdrawn from the study, and all AEs associated with BMD loss (e.g., osteoporosis, osteopenia, fractures) and all ADRs will be collected irrespective of treatment discontinuation.

All AEs will be summarised in tabulated forms in the interim safety analysis and final study report.

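### The only SAP deadline is study database lock, at least six months after the first interim report, so choices left to the SAP can be fixed after interim outcomes are seen

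*Protocol*

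**What the plan says.** **SAP deadline.** Section 9.7.1: "The SAP will be finalised before study database lock". Section 9.7.3.5: "Further details will be specified in the SAP, which will be finalised before study database lock". The data-analysis paragraph of the abstract gives the same deadline. Annex 15.1 lists the SAP as in progress.

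**Timeline.** Section 6: "Start of data collection (FPFV) Q1/Q2 2026" and "End of data collection (LPLV) Q3/Q4 2029". Section 9.7.1: "The final data analysis will be performed after the study has been completed and the database has been declared to be clean". Section 9.7.5: "The first interim report is expected in Q3/Q4 2028".

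**Interim content.** Section 9.7.5 does not list it. Section 11.3 does for adverse events: "All AEs will be summarised in tabulated forms in the interim safety analysis and final study report".

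**Left to the SAP.** In 9.7.3.3, sensitivity analyses using criteria "to select DXA scans that ensure their comparability will be performed to evaluate the primary endpoint" are to be detailed in the SAP. So are the strata (9.7.2), confounder handling (9.7.4) and the event term specifications (9.7.3.4).

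**The concern.** Leaving detail to an SAP is normal. The problem is the event to which the deadline is tied. The study is open and has one group, so nothing is masked when interim tables are produced. With no comparator, each result is a single proportion or rate, and its definition largely determines the number. If term lists, strata or scan criteria are settled once the tables have been seen, a reader of the final report cannot tell whether a definition was chosen before or after its effect was known. A difference between the interim and final reports could also come from changed definitions and not from new data.

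**Working it through.** The check is one of sequence and wording. No sample-size figure enters.

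**1. Inputs (section 6; recruitment length also in 9.1)**

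| Event | Stated date | Calendar span |
|---|---|---|
| First patient first visit | Q1/Q2 2026 | Jan to Jun 2026 |
| First interim report | Q3/Q4 2028 | Jul to Dec 2028 |
| Last patient last visit | Q3/Q4 2029 | Jul to Dec 2029 |
| Recruitment per country | up to 18 months | – |

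**2. Earliest possible lock.** The final analysis needs a completed study and a clean database, so study database lock cannot precede the end of data collection. The earliest date is July 2029.

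**3. Interim report to end of data collection**
- Shortest: end Dec 2028 to start Jul 2029 = 6 months.
- Longest: start Jul 2028 to end Dec 2029 = 18 months.

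The data cut comes before the report, so the true gap is longer. Section 6 also lets data collection be prolonged, which would move lock later still.

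**4. Could long-term data exist at the interim?**
- First patient: shortest, end Jun 2026 to start Jul 2028 = 24 months; longest, start Jan 2026 to end Dec 2028 = 36 months.
- Last patient in the first country, if recruitment takes the full 18 months: 24 − 18 = 6 months to 36 − 18 = 18 months.

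These figures use the report date, so follow-up at the cut is somewhat shorter. Countries that launch later will have less. Even so, some patients can have passed 12 months of treatment.

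**5. What the interim will show.** Adverse-event tables are explicit in 11.3. The liver, mood, cancer and QT endpoints in 9.1.2 are largely incidence rates of adverse events, so their raw material is in those tables. Section 9.2.4 also speaks of interim analysis datasets and outputs. BMD is less certain: 9.1 sets BMD results against the literature when reports (plural) are written, and nothing confines BMD to the final report, but nothing expressly places it in the interim.

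**6. How open each choice is**

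| Choice | Section | State in the protocol |
|---|---|---|
| DXA selection, sensitivity analyses of the primary endpoint | 9.7.3.3 | Machine type as an example; rest to the SAP |
| Scan comparability for BMD change | 9.7.3.4 | Open list of examples |
| Strata | 9.7.2 | Some named; other clinical characteristics to the SAP |
| Confounder handling | 9.7.4 | Stratification if applicable; details to the SAP |
| Cancer terms | 9.7.3.4 | Two diagnoses named; contents to the SAP |
| QT terms | 9.7.3.4 | Event types named; contents to the SAP |
| Liver terms | 9.7.3.4, 15.1 | Preliminary list exists; completion to the SAP |
| Mood terms | 9.1.2, 9.7.3.4 | Ten preferred terms named; little left open |

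No section requires a final SAP before the interim, so every open item above may lawfully be settled after the interim tables exist.

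**The case against.** **Database lock is an outer limit.** Nothing says the interim will run without an SAP, and the SAP may be final long before lock. That is true and cannot be judged from the protocol. The point is only that the protocol permits the wrong order.

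**The study is descriptive.** Section 9.5 rules out a formal hypothesis test, so no error rate is at stake. This stands and keeps the point minor.

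**Safety reports reach the sponsor throughout (11.4, 11.5).** A deadline at the interim data cut would therefore not make the rules fully blind to results. This also stands, and is why a date before the first patient is better. The earlier cut still puts the rules ahead of the first compiled outcome tables.

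**The term lists are mostly settled.** This is right for mood and partly right for liver. For all four event groups the SAP specification is also tied to the MedDRA version current at analysis, and some of that is legitimate version updating. Real but limited freedom remains for cancer, QT and the completion of the liver list.

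**Stronger readings the protocol does not support**
- A reader might infer that the SAP decides which DXA scans count in the main primary analysis. The criteria that 9.7.3.3 hands to the SAP concern sensitivity analyses only. For the main analysis the protocol fixes more than 12 months of treatment and available z-scores (9.7.3.3), the −2 threshold (9.1.2), the lowest of the site values (9.5) and no imputation (9.7.1).
- A reader might size the problem by contrasting one skeletal site with the lowest of three. Section 9.5 has already made that choice, so the contrast does not measure what a late SAP leaves open.
- A reader might say the sponsor will see the primary proportion in 2028. That is possible, but it is an inference.

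**Conclusion.** The point holds as a minor one. The stated deadline falls at least 6 months, and up to 18 months or more, after the first interim report. Adverse-event outcomes will have been tabulated by then, and BMD results may have been. The protocol therefore allows the open choices in the table to be made with outcomes in hand, and allows the interim and final reports to differ in definition.

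This rests on the milestone dates being kept and on lock following the end of data collection. It does not assume that the sponsor will finish the SAP late. No effect on any estimate can be put in figures from the protocol, and the sample-size and precision figures are untouched. The harm is data-driven definition, not type I error.

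**What to change.** In the abstract, 9.7.1 and 9.7.3.5, replace the deadline with: *The SAP will be finalised before the data cut for the first interim analysis (preferably before first patient in); later changes, other than MedDRA version updates, are dated, justified and labelled post hoc in the reports.*

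The SAP finalised by that date should cover the open items, including the comparability criteria for BMD change that 9.7.3.4 gives only as examples.

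The cost is three changed sentences and writing the same document sooner. Patients, visits, data collection and sample size are unaffected.

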### **9.7.2 Study Population**

All analyses will be performed for the total study population (overall analysis). Separate analyses for each participating country will be provided if patient numbers are sufficient and if required for local reasons. In addition, data will be stratified whenever reasonable and dependent on the number of patients by the following parameters: country, age, race, dosing regimen, long- vs. short-term use of Yselyt®, and other relevant clinical characteristics and will be specified in the SAP.

### **9.7.3 Analysis of Variables**

#### **9.7.3.1 Analysis of Demography, Disease History, Comorbidities, Prior and Concomitant Medication and Other Baseline Data**

Baseline data such as patient demographics, comorbidities, prior and concomitant medication will be described by presenting frequency distributions and/or basic summary statistics.

Stratified analyses to estimate possible protective or damaging effects through prior medication or concomitant medication will be conducted if the sample size is sufficient and will be detailed further in the SAP.

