#### **Follow-up visit(s) for patients who experienced BMD decrease or osteoporosis during the study**

Patients who discontinued treatment with Yselty® but had BMD decrease or osteoporosis during the study should be observed in the study for up to 24 months after the last administration of Yselty®. Documentation of further visits by the physician during the further follow-up period will be limited to BMD assessments and relevant concomitant medications. For AE reporting please see section 11.3.

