### **9.3.3 Prior and Concomitant Medication**

Medication taken before study start (initiated and stopped before study start) are defined as prior medications. All medication taken in addition to the prescribed Yselty® dosing regimen for any indication (either initiated before study start or during the study) are defined as concomitant medications.

Information on prior treatment with ABT, prior treatments for fibroids (labelled and off-label), previous GnRH-agonist treatment, and previous systemic treatment (glucocorticoids, aromatase inhibitors, thiazolinediones, thyroxine, drugs targeting the immune system (such as calcineurin inhibitors and antiretroviral drugs), selective serotonin reuptake inhibitor anticonvulsants, loop diuretics, heparin, and proton pump inhibitors) is to be collected as part of the enrolment data collection. Additionally, all relevant concomitant medication taken at enrolment and during the study will be recorded. Relevant concomitant medication includes anything influencing BMD loss (list defined for previous systemic treatment). Medications which may impact on liver enzyme increase or QT prolongation will be specified in the SAP.

Information on medication (including changes) will be collected in the categories stated below:

- Trade name or international non-proprietary name
- Start date (at least year)
- Stop date or “continued”
- Daily dose, if applicable
- Indication (prespecified categories: treatment of concomitant disease/treatment of AE/other)

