BMD will be displayed as absolute and relative change in density ( $\text{g}/\text{cm}^2$ ) and absolute value and relative change of z-scores and t-scores over time by means of summary statistics; e.g., DXA scans performed at baseline (if available) vs. timepoint 1 – 1st year (+/-6 months) after treatment initiation, timepoint 1 – 1st year (+/-6 months) after treatment initiation vs. DXA scans performed at timepoint 2 – 2nd year (+/-6 months), where the measurements are at least 6 months apart. This is continued in the same way for further years if the sample size is at least 5 patients. Changes are only analysed if e.g., the machine types, the location of the scan and other criteria that allow comparability are consistent. A subgroup analysis of t-scores for the subgroup of postmenopausal patients and of z-scores in the subgroup of premenopausal patients will be conducted, if sample size allows. Additionally, patients who experienced BMD decrease during the study but continued to be observed in the study, regardless of the reason for which Yselty® treatment was discontinued, will be investigated as a separate subgroup. This subgroup analysis will include the presentation of both absolute value and relative change of z-scores and t-scores after discontinuation. If the sample size permits, this subgroup will be stratified based on whether alternative treatments administered after discontinuation may also lead to a decrease in BMD (refer to “previous systemic treatments” in section 9.3.3).

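### Section 9.7.3.1 plans to estimate effects of concomitant medication by stratification, but the protocol's definition admits drugs started after, or because of, the outcome

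*Protocol*

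**What the plan says.** Section 9.7.3.1 states the aim: "Stratified analyses to estimate possible protective or damaging effects through prior medication or concomitant medication will be conducted if the sample size is sufficient". The sentence ends by leaving further detail to the SAP. The sentence before it places this medication among baseline data: "Baseline data such as patient demographics, comorbidities, prior and concomitant medication will be described".

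Section 9.3.3 defines the term more widely. Drugs taken besides the Yselty regimen "either initiated before study start or during the study) are defined as concomitant medications". Recording runs through follow-up: "Additionally, all relevant concomitant medication taken at enrolment and during the study will be recorded". On scope it says "Relevant concomitant medication includes anything influencing BMD loss (list defined for previous systemic treatment". Each entry carries a start date, for which the year alone suffices, and an "Indication (prespecified categories: treatment of concomitant disease/treatment of AE/other".

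Two follow-up rules in section 9.2.6 matter. Women who stop Yselty after a BMD decrease or osteoporosis "should be observed in the study for up to 24 months after the last administration of" Yselty, with BMD assessments and relevant concomitant medication still documented. For other women, observation ends when Yselty is discontinued.

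Section 9.7.4 names site and baseline disease severity as possible confounders. It does not mention the timing of medication relative to outcome.

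**The concern.** A stratum can support a statement about a drug's effect only if membership is settled before the outcome. If the term is applied as 9.3.3 defines it, membership can be settled afterwards, in two ways.

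- **Reverse causation.** A drug begun because of a low DXA result or an adverse event puts that patient in the user stratum together with the outcome that prompted the prescription. The drug then looks damaging.
- **Time under observation.** A woman must be observed long enough to start a drug. If the event ends observation, early cases cannot become users and the drug looks protective. If cases are observed longer than non-cases, they have more time to become users and the drug looks damaging.

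At stake is the reading of a stratified table in a post-authorisation safety report whose primary outcome is BMD. The apparent effect could come from prescribing order and length of follow-up alone.

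**Working it through.** **The plan's own figures.** The stratified analysis has no stated figure. Table 2 supplies the dropout assumption and reproduces. With n = 1,000 × 0.8^k, n is 800, 640, 512 and 409. With half-width 1.96 × √(0.025 × 0.975 / n), the results are 1.08%, 1.21%, 1.35% and 1.51%, against the printed 1.10%, 1.20%, 1.35% and 1.50%.

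**Hand check of reverse causation.** Let q = 0.0228 be the share of a standard normal below −2 (section 9.5 takes 2.5%). Let a be the probability that a woman below −2 is started on an inert drug, and b the same for other women. Assume a = 10% to 30% and b = 2% to 5%; neither is in the protocol.

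- Users: share below −2 = q·a / [q·a + (1 − q)·b]
- Non-users: share below −2 = q(1 − a) / [q(1 − a) + (1 − q)(1 − b)]

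Mildest corner (a = 10%, b = 5%): 0.00228 / (0.00228 + 0.04886) = 4.5% in users, against 0.02052 / (0.02052 + 0.92834) = 2.2% in non-users. Strongest corner (a = 30%, b = 2%): 0.00684 / (0.00684 + 0.01954) = 26%, against 0.01596 / (0.01596 + 0.95766) = 1.6%.

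**Simulation with follow-up.** The drug has no effect. Inputs from the protocol are 20% annual dropout and up to four years of observation. Assumed inputs are event rates of 1% to 5% per year, drug-start rates of 5% to 30% per year, and prescribing after the event in 10% to 60% of cases (background start 5% per year). Patients are classed as ever or never having started the drug. The true ratio is 1.

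| Situation | Rate ratio, ever/never | Ratio of proportions |
|---|---|---|
| Drug prescribed after event, 10% of cases | about 1.1 | 1.4–1.5 |
| 30% of cases | 2.7–2.9 | 3.2–3.7 |
| 60% of cases | 7–9 | 8–11 |
| Unrelated drug, event ends observation or recording | 0.35–0.48 | 0.59–0.66 |
| Unrelated drug, recording continues after event | 0.99–1.01 | 1.33–1.64 |

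A separate run of the fourth situation, with an event rate of 0.10 per year, staggered entry over 18 months and a 42-month study, gave rate ratios of 0.43 to 0.49.

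**Primary endpoint with an unrelated drug.** The outcome is any annual scan with z below −2, compared as a ratio of proportions.

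- Observation not altered by a low scan: 1.05–1.20.
- Yselty stopped after a low scan and 24 further months recorded, as in section 9.2.6 (a low scan being taken to count as a BMD decrease): 1.14–1.34.
- Observation ended at the low scan, contrary to 9.2.6: 0.45–0.82.

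**Check of the remedy.** Counting exposure only from the drug's start, and only outcomes after it, returns rate ratios of 0.98 to 1.02 in the simulated event scenarios.

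**The case against.** The strongest reply is that the protocol fixes no ever/never classification. Section 9.7.3.1 defers detail to the SAP, and its heading and first sentence treat concomitant medication as baseline data. On that reading the strata are already close to the remedy. The study is descriptive, the analysis depends on sample size, and section 9.7.4 urges caution about confounding.

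This stands in part. The bias is a possibility left open, not a certainty. But the aim of estimating effects and the definition of the term are protocol text, and the stratification sentence does not repeat the baseline restriction. One input is also settled at data collection: where only the year of start is recorded, no SAP can place the drug before or after a scan in that year.

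Three stronger readings are tempting and are not supported.

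- *Unrelated drugs will look protective.* This requires the event to end observation or recording. It can happen for an adverse event that leads to stopping Yselty without BMD decrease. It does not fit BMD outcomes, where 9.2.6 keeps cases under observation.
- *Drugs given for bone loss will certainly be in the strata.* The list in 9.3.3 names no anti-osteoporosis drug. Their capture rests on the general wording about anything influencing BMD loss and on the adverse-event indication category.
- *The post-discontinuation strata in 9.7.3.4 share the fault.* There, "this subgroup will be stratified based on whether alternative treatments administered after discontinuation may also lead to a decrease in BMD". Everyone in that subgroup has already had a BMD decrease, so that decrease cannot separate users from non-users. The calculations above do not address that analysis.

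**Conclusion.** The point holds as an open route to bias. Sections 9.7.3.1 and 9.3.3, read together, permit effect strata that include drugs started after the outcome, and nothing in the protocol closes this. With no drug effect, a drug started because of the outcome gives a rate ratio of about 1.1 to 9. An unrelated drug gives about 0.35 to 0.49 when the event ends observation. For the BMD endpoint with continued follow-up, the ratio of proportions is about 1.1 to 1.3, towards damaging.

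These sizes rest on assumed event, drug-start and prescribing rates and on an ever/never comparison, which the SAP may not adopt. They show the direction and possible scale of the bias; they do not predict this study's results. The analysis serves none of the numbered objectives, so the point affects how a supporting table is read and not the primary estimate.

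**What to change.** In section 9.7.3.1, limit effect strata to prior medication and medication ongoing at the first Yselty dose. For drugs started later, count exposure only from the recorded start date and only outcomes after it, and use the indication already collected to flag drugs given for an event. If this is not wanted, replace the aim of estimating effects with one of describing outcomes by medication use.

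In section 9.3.3, ask for at least month and year of start for BMD-relevant drugs begun during the study. This should be settled before data collection begins, planned for Q1/Q2 2026, because it cannot be reliably repaired in the SAP.

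The cost is a few protocol sentences, a tighter date field for one group of drugs, some extra programming and smaller strata, which may leave some comparisons too small to present. The post-discontinuation strata in 9.7.3.4 need no change on this account.
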